# **9 OVERALL STATISTICAL CONSIDERATIONS**

## **9.1 Sample Size Computation**

Approximately 90 subjects (30 subjects per treatment group) will be randomized into 1 of 3 treatment groups: gemcabene 300 mg, gemcabene 600 mg or placebo.

A sample size of 30 randomized subjects in the gemcabene 300 mg group, 30 randomized subjects in the 600 mg group and 30 randomized subjects in the placebo group is expected to provide 80% power to detect a difference of 35% in the percent change in TG from baseline to EOS between either of the gemcabene treatment groups and the placebo group. This calculation is based on a 2-sided t-test at the 5% level of significance ( $\alpha = 0.05$ ), a common standard deviation (SD) of 43, and a drop-out rate of 15%.

In this Phase 2 study, both the gemcabene 300 mg and the 600 mg treatment groups will be compared to placebo separately using a 5% significance level ( $\alpha = 0.05$ ). No statistical adjustment will be used for these two comparisons of the primary efficacy endpoint.

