## 9.2 General Conventions

In general, categorical variables will be summarized using frequency and percentages whereas mean, SD, median, minimum, and maximum will be used to summarize continuous variables.

For efficacy parameter values that are collected as “< x.x” or “> x.x”, the numerical portion will be summarized, but the actual collected values will be reported in the listings. Safety results collected as “< x.x” or “> x.x” will not contribute to the summary tables, and will only be displayed in the listings.

Decimal precision for continuous variables will be based on the mean value; the median will contain the same number of decimal places as the mean, the SD will contain one more decimal place than the mean, and the minimum and maximum will contain one less decimal place than the mean. Typically, the mean will contain one more decimal place than actual values but decimal precision may vary in order to obtain an organized and understandable table or listing.

The first day of administration of randomized study medication (first dose) is defined as Study Day 1 or Day 1. All other study days will be computed relative to Day 1. For events on or after Day 1, study day for a particular event will be calculated as:

$Date_{event} - Date_{first\ dose} + 1$ . For events before Day 1, study day for a particular event will be calculated as:  $Date_{event} - Date_{first\ dose}$ . Day 0 will not be used.

All statistical testing will be 2-sided and performed at the alpha = 0.05 level. No multiplicity adjustments will be made for testing multiple secondary and exploratory efficacy outcomes. Given the large number of secondary and exploratory efficacy outcomes, p-values associated with such outcomes will be considered descriptive. As it is possible that some significant results could occur due to chance alone, undue consideration will not be given to isolated significant differences; rather, interpretation will be made based on patterns of significant differences and consistency with the primary outcome.

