## 11 EFFICACY PARAMETERS

### 11.1 Primary Analysis

The primary efficacy endpoint (percent change in fasting serum TG from baseline to EOS) will be analyzed using ANCOVA on rank-transformed data (i.e., ranked ANCOVA) with percent change from baseline to EOS in TG (converted to ranks) as the dependent variable; treatment and baseline statin (yes or no) as factors; and ranked baseline fasting serum TG as a covariate. The ranked ANCOVA is used due to the expected non-normality historically observed with triglyceride data. The primary analysis will be performed using the FAS. The null hypotheses to be tested are the following:

- $H_1$ : there is no difference in the percent CFBL to EOS in fasting serum TG between gemcabene 300 mg and Placebo
- $H_2$ : there is no difference in the percent CFBL to EOS in fasting serum TG between gemcabene 600 mg and Placebo

A 2-sided test with a significance level of 0.05 will be used for the comparison of the gemcabene 300 mg and 600 mg groups separately to the placebo group. No statistical adjustment will be performed for multiplicity in this Phase 2 study. Note that EOS is defined using LOCF as indicated in [Section 9.4](#). The median, interquartile range, and associated p-value from the ranked ANCOVA will be presented for each treatment group.

```
proc glm data=data;
  class TRT(ref="Placebo") Statin;
  model r_pctCFBL = TRT Statin r_Base / solution;
  lsmeans TRT / stderr pdiff;
run;
```

Where a ranked ANCOVA is used, ranking will be done on the outcome variable and baseline covariate. All values will be ranked by visit regardless of treatment group, with ties receiving the average of the ranks.

Ranked ANCOVA is generally used when the statistical assumptions for parametric ANCOVA, including normality and homoscedasticity (equal variances), are not met, therefore these formal assumptions will not be checked for the ranked ANCOVA analyses. The assumption of homogeneity of regression slopes across treatment groups (parallel slopes) will be investigated by including the interaction between baseline fasting serum TG and treatment group in the model explicated previously. If results indicate that the interaction between baseline fasting serum TG and treatment group is not significant, the assumption of parallel slopes will be considered met. If the assumption of parallel slopes is clearly violated, the final model may be adjusted.

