## 11.3 Secondary Analysis

Secondary analyses will be conducted using the methodology detailed below. All secondary analyses will be conducted using the FAS population (or the specific subgroup within the FAS population, eg, diabetic subjects).

The secondary endpoints are as follows:

- CFBL and percent CFBL to Weeks 2, 6, 10, 12, and EOS in fasting serum TG;
- CFBL and percent CFBL to Weeks 2, 6, 10, 12, and EOS in TC, non-HDL-C, HDL-C, and VLDL-C;
- CFBL and percent CFBL to Weeks 10, 12, and EOS in LDL-C LDL-TG, VLDL-TG, HDL-TG;
- CFBL and percent CFBL to Weeks 10, 12, and EOS in Apo B, ApoA-I, ApoA-II, ApoC-II, ApoC-III, and ApoE;
- CFBL and percent CFBL to Week 12 in lipoprotein size and particle number (NMR);
- CFBL and percent CFBL to Weeks 10, 12, and EOS in hsCRP, IL-6, SAA, adiponectin, and fibrinogen; and
- Percent of subjects achieving a TG value < 500 mg/dL (5.65 mmol/L) at Weeks 10, 12, and EOS.

Continuous secondary efficacy endpoints that measure CFBL and percent CFBL will be analyzed using ranked ANCOVA with CFBL or percent CFBL in the respective parameter as the dependent variable; treatment, baseline statin (yes or no) and qualifying TG stratum ( $> 880$  mg/dL or  $\leq 880$  mg/dL) as factors; and the respective ranked baseline as a covariate. Qualifying TG stratum will not be included as a factor in secondary ANCOVA models where TG is the parameter of interest (dependent variable). For the EOS time point, EOS is defined in [Section 9.4](#) or all other time points, missing values will be imputed using LOCF, with the last on-treatment value carried forward to that time point.

Secondary efficacy endpoints that are continuous will be analyzed using ranked ANCOVA and secondary efficacy endpoints that are binary will be analyzed using logistic regression.

The output from each ranked ANCOVA will be consistent with the primary efficacy model.

The percent of subjects achieving a TG value < 500 mg/dL (5.65 mmol/L) at Weeks 10, 12, and EOS will be analyzed using a logistic regression with treatment, baseline statin use (yes or no), and baseline TG value as independent factors. The percent of subjects in each treatment group achieving a TG value < 500 mg/dL, and the odds ratios (ORs) with 95% confidence intervals and p-values will be presented to compare gemcabene 300 mg and gemcabene 600 mg separately with the placebo group.

The SAS code used to conduct a logistic regression model is provided below:

```
proc logistic data=data;

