  class TRT(ref="Placebo") Statin;
  model Outcome(event="event")= TRT Statin Base / expb;
run;
```

Descriptive statistics for all secondary efficacy parameters will also be provided by visit.

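### The SAP's logistic code for the TG < 500 mg/dL responder endpoint gives no dose-versus-placebo p-values: by default its EXPB estimates and Wald tests compare each dose with the average of all three arms

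*SAP*

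**What the plan says.** For the percentage of subjects reaching TG < 500 mg/dL at Weeks 10, 12 and EOS, SAP 11.3 specifies a logistic regression on treatment, baseline statin use and baseline TG. It states that "odds ratios (ORs) with 95% confidence intervals and p-values will be presented" in order to "compare gemcabene 300 mg and gemcabene 600 mg separately with the placebo group". The protocol (Synopsis and 9.3.1.2) makes the same commitment.

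The SAS code that follows has two working lines: "class TRT(ref='Placebo') Statin" and "model Outcome(event='event')= TRT Statin Base / expb". It has no PARAM= option and no ODDSRATIO, CONTRAST, ESTIMATE or LSMEANS statement. The SAP does not say which output table supplies the reported odds ratio or p-value.

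The code for the primary analysis in SAP 11.1 does request the treatment comparisons explicitly: "lsmeans TRT / stderr pdiff". SAP 9.2 sets the testing rule: "All statistical testing will be 2-sided and performed at the alpha = 0.05 level".

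**The concern.** In PROC LOGISTIC the CLASS statement uses effect coding unless told otherwise. REF= then only decides which level is coded -1 and does not produce reference-cell coding. Each treatment coefficient is that dose's log-odds minus the unweighted mean log-odds of placebo, 300 mg and 600 mg. EXPB exponentiates that coefficient, and the Wald p-value beside it tests it against zero. Neither is a comparison with placebo.

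The threshold of 500 mg/dL is the one in the stated indication (Protocol 3.2), so this responder result will be read closely. The error also depends on the other active arm, because a strong 300 mg result raises the three-arm average and pulls the 600 mg coefficient down. Protocol 1.2 expects that pattern: at baseline TG of 500 mg/dL or more it cites TG lowering of 50-60% at 300 mg and about 30% at 600 mg. A real 600 mg effect could be reported as absent, or a null one as harmful.

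**Working it through.** **Plan's own figure.** The documents give no power figure or response rates for this endpoint. The only design figure is 30 per arm for the primary endpoint (SAP 9.1). It reproduces: a two-sided t-test with difference 35, SD 43 and alpha 0.05 needs 25 evaluable per arm (power 80.5%), and 25/0.85 = 29.4, rounded up to 30. The illustrations below use 30 per arm; the response rates are assumptions.

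**Formulas.** Let L be an arm's logit and V = 1/events + 1/non-events its variance.

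- Effect coding: b(dose) = L(dose) − mean of the three L. Its variance is (4/9)·V(dose) + (1/9)·(sum of the other two V).
- Against placebo: log OR = L(dose) − L(placebo), with variance V(dose) + V(placebo).
- Link: log OR against placebo = 2·b(dose) + b(other dose).

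**Worked example: responders 6/30, 21/30, 14/30 (placebo, 300 mg, 600 mg), no covariates.**

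- Logits: ln(6/24) = −1.386; ln(21/9) = 0.847; ln(14/16) = −0.134. Mean = −0.224.
- Variances: 0.208, 0.159, 0.134.
- 300 mg, as coded: b = 1.071, SE 0.330, exp(b) = 2.92, p = 0.001. Against placebo: log OR 2.234, SE 0.606, OR 9.33, p = 0.0002.
- 600 mg, as coded: b = 0.091, SE 0.317, exp(b) = 1.09, p = 0.77. Against placebo: log OR 1.253, SE 0.585, OR 3.50, p = 0.032.
- Link check for 600 mg: 2 × 0.091 + 1.071 = 1.253.

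**Other assumed patterns, 30 per arm, same formulas.**

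| Placebo / 300 / 600 | Dose | exp(b) as coded (p) | OR vs placebo (p) |
|---|---|---|---|
| 20% / 50% / 50% | each | 1.59 (0.138) | 4.00 (0.018) |
| 20% / 60% / 40% | 300 mg | 2.38 (0.006) | 6.00 (0.002) |
| 20% / 60% / 40% | 600 mg | 1.06 (0.86) | 2.67 (0.096) |
| 20% / 70% / 20% | 600 mg | 0.47 (0.04) | 1.00 (1.0) |

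**With the SAP's covariates.** In one simulated dataset of 90 (responders 6, 15 and 15 of 30; statin and baseline TG in the model), effect coding gave 1.54 (p = 0.168) for 300 mg and 1.63 (p = 0.123) for 600 mg. Reference coding gave OR 3.87 (95% CI 1.22 to 12.3, p = 0.021) and 4.08 (95% CI 1.29 to 13.0, p = 0.017). The log-likelihood was −55.946 under both codings, so the fit is the same and only the meaning of the coefficients changes.

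**Repeated trials (1,500 simulated trials, 30 per arm, covariates included).**

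- Placebo 25%, 300 mg 65%, 600 mg 25%: the 600 mg row is significant with exp(b) below 1 in 36.8% of trials. The correct test against placebo rejects in 5.1%.
- Placebo 25%, both doses 55%: rejection falls from about 61-63% for the placebo comparison to 25-28% for the coded one.

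**The case against.** The same call also prints a default table of odds ratio estimates, whose ratios and Wald intervals are dose versus placebo under either coding. Two of the three promised quantities are therefore correct in the same run. A programmer who needs an interval would have to go to that table, because EXPB gives only point estimates. The prose is also unambiguous about the comparison, the endpoint is secondary, SAP 9.2 treats secondary p-values as descriptive, and with no effect in either dose both codings reject at about 5%. Finally, the point depends on a SAS default that the documents do not state.

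Most of this stands as a limit on the consequence. It does not supply the missing p-values: the default odds ratio table carries none, and the only p-values the code prints by dose test a different contrast. EXPB suggests that the author expected the parameter table to give the comparison with placebo. A report could then pair a correct odds ratio with the wrong p-value. In the worked example that would be OR 3.50 with an interval of 1.11 to 11.0 (exp(1.253 ± 1.96 × 0.585)) beside p = 0.77. A careful reader might notice, but the plan should not rely on that. The software default can be confirmed in the Class Level Information output of any run.

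**Conclusion.** The concern holds. Run as written, the code does not deliver the dose-versus-placebo p-values that SAP 11.3 and Protocol 9.3.1.2 promise, and the EXPB column is not the odds ratio against placebo. The odds ratios and intervals can be obtained correctly from the default table, but the SAP does not direct the reader there.

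The size depends on response rates that the documents do not give. In the illustrations a 600 mg odds ratio of 3.50 (p = 0.032) appears as 1.09 (p = 0.77), and a 600 mg arm identical to placebo appears worse at p = 0.04. The conclusion assumes that PROC LOGISTIC's default effect coding is in force and, for the wrong estimates as opposed to the wrong p-values, that EXPB is what gets reported. The defect is confined to the code for one secondary endpoint at three time points. It should be corrected, but it does not threaten the primary result.

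**What to change.** Add `/ param=ref` to the CLASS statement, keeping placebo as the reference level. The treatment coefficients then become log odds ratios against placebo, EXPB prints those odds ratios, and the Wald p-values test the promised comparisons. An alternative is to keep the default coding and add `oddsratio TRT / diff=ref` with matching ESTIMATE statements for the p-values. In either case, state in SAP 11.3 which output tables supply the odds ratio, the interval and the p-value, so that all three refer to the same contrast.

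The cost is one line of code and one sentence of text. The model, its fit, the data and the sample size are unchanged, and there is no statistical downside.

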## 11.4 Exploratory Analysis

Cl

CI

Descriptive statistics will also be provided by visit

## 12 SAFETY AND TOLERABILITY

Safety will be assessed through analysis of AEs, clinical laboratory assessments, ECGs, vital signs, and physical examinations for the SAS using descriptive statistics. Observed case data will be used. Additionally, summaries of safety data will be displayed by treatment group. Treatment group will be based on the treatment each subject actually received regardless of randomized treatment group. All safety data will be presented in listings.

### 12.1 Adverse Events

AEs will be coded using Medical Dictionary for Regulatory Activities (MedDRA) version 19.1. All AE tables will be summarized for overall by treatment group and by stable statin use at baseline (according to the CRF) within treatment group. Except for the AE overview table and summaries of serious adverse events (SAEs) and AEs resulting in death (both of which will include all AEs), AE tables will only include summaries of treatment-emergent adverse events (TEAEs). A TEAE is defined as an AE with start date on or after the first dose date and less than 30 days after the last dose date. If AE start date is missing, the AE is assumed to be a TEAE. An AE overview table containing the frequency and percent of the following will be summarized by treatment group, and treatment group within each baseline statin (yes or no):

- Number of subjects with at least one TEAE, drug-related TEAE, SAE, drug-related SAE;
- Number of subjects who discontinued study treatment due to TEAE, drug-related TEAE, SAE, and drug-related SAE;
- Number of subjects who discontinued the study due to a TEAE; and
- Number of subjects who had a study treatment interruption due to a TEAE;
- Number of deaths and deaths due to a drug-related TEAE.

Additionally, the following will be summarized by treatment group, and treatment group within each stratum:

- TEAEs by system organ class (SOC) and preferred term (PT);
- TEAEs by descending PT ;
- TEAEs by SOC, PT, and maximum severity;
- Related TEAEs by SOC and PT;

- Related TEAEs by descending PT;
- SAEs by SOC and PT;
- Related SAEs by SOC and PT;
- TEAEs leading to treatment discontinuation by SOC and PT;
- Related TEAEs leading to treatment discontinuation by SOC and PT; and
- AEs that resulted in death by SOC and PT.

Summaries of SOC and PT will be sorted alphabetically by SOC and by decreasing frequency of PT in the total column for the gemcabene 600 mg group, followed by the 300 mg group, then placebo.

Note that the overview of AEs will be provided separately for the double-blind treatment period and follow-up period, to allow for a delivery of the double-blind data only during the database freeze.

If a subject has more than one TEAE at a given level (eg, SOC and PT), the subject will only be counted once within that level. When summarizing TEAEs by maximum severity or causality, at each level of summarization, subjects who report one or more TEAEs within that level are only counted once at that level using the event of greatest severity (in severity tables) or strongest relationship to study drug (in causality tables). All tables will show the number and percent of subjects with at least one TEAE (or SAE, per the criteria on the table). For example, the table of related SAEs will include a row for number and percent of subjects with at least one related SAE. Additionally, a drug-related TEAE is defined as a TEAE with an assigned relationship of “related.” A listing containing all AEs (pre-treatment and TEAEs) will be created; AEs that are not treatment-emergent will be flagged as non-treatment-emergent. Additionally, a listing containing AEs missing severity or relationship to the study drug will be provided.

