#### 1.4 Risk/Benefit

The clinical program conducted to date has demonstrated that gemcabene is generally well tolerated. A total of 895 healthy adult subjects and subjects with various underlying conditions (including dyslipidemia, osteoarthritis, and hypertension) have been exposed to a minimum of at least 1 dose of gemcabene at doses ranging from 150 mg to 1500 mg QD. This includes 837 subjects who received multiple doses of up to 900 mg for up to 12 weeks. This also includes 292 subjects (150 subjects on high-intensity) on gemcabene in combination with a statin. Safety of these subjects was evaluated by adverse event monitoring, clinical laboratory assessments, electrocardiograms (ECGs), physical examinations, and vital sign assessments.

No significant drug-drug interactions have been observed with simvastatin (80 mg), atorvastatin (80 mg), or digoxin (0.25 mg). No clinically relevant effect on QTc or blood pressure has been observed.

Across all clinical studies, the majority of treatment-emergent adverse events were mild to moderate in intensity. The most common adverse events reported included headache, asthenia (feeling of weakness), nausea, dizziness, dyspepsia (upset stomach), infection, abnormal bowel movements, myalgia, and abnormal kidney function tests. Ten subjects (1%) reported a treatment-emergent serious adverse event (SAE) across all previous studies. None of these SAEs were considered treatment-related. There were no deaths.

Small mean increases in serum creatinine and blood urea nitrogen (BUN) have been observed in some studies. These changes appeared within the first 2 to 4 weeks and did not appear to increase further over time. An iohexol clearance study showed that glomerular filtration rate (GFR) slightly decreased and was associated with a slight increase in serum creatinine. There was no indication of proteinuria or hematuria identified in any subject. There were no significant changes observed in urine protein, which seems to indicate that gemcabene does not cause tubular or glomerular injury. And, the increase was reversible with all creatinine values returning

to baseline within approximately 2 weeks of cessation of gemcabene, suggesting a vascular effect and not renal injury.

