### 6.2 Pre-Screening Visit

**Only subjects requiring a Wash-Out Period will participate in the Pre-Screening Visit.**

**Subjects must have a Pre-Screening TG value  $\geq 350$  mg/dL and  $< 1800$  mg/dL before washing out of current TG-lowering therapies and proceeding to S1.**

A Wash-Out Period will be required for eligible subjects taking any lipid-regulating therapies or supplements, with the exception of statins or ezetimibe. For subjects requiring a Wash-Out Period, the Pre-Screening Visit will be their first study visit and will occur prior to the Screening Visit based on the duration of the Wash-Out Period required. Specifically, PCSK9 inhibitors will require an 8-week Wash-Out Period, fibrates will require a 6-week Wash-Out Period, and niacin, OMG-3, bile acid sequestrants or other lipid-regulating therapies will require a 4-week Wash-Out Period prior to the Screening Visit. If the subject needs to be washed off more than one lipid-altering medication; the medication that requires the longest Wash-Out Period will be the default. For example, if a subject is taking OMG-3 and fibrates, then the subject would undergo a six-week Wash-Out Period.

The Wash-Out Period will only be initiated after inclusionary lab values are received and reviewed.

The following procedures will be performed at the Pre-Screening Visit:

- Obtain informed consent;
- Conduct eligibility assessment based on inclusion/exclusion criteria;
- Obtain medical/surgical history and demographics;
- Obtain concomitant medications; including all anti-diabetes pharmacologic therapy for subjects with Type 2 diabetes
- Perform full physical examination;
- Record vital signs, height, weight and calculate BMI;
- Collect urine sample;
- Perform urine pregnancy test (for women of child-bearing potential only);
- Obtain blood sample for the following:

- Safety chemistry panel, coagulation, and hematology;
- TSH, HbA1c, and serology (HBV, HCV, and HIV); and
- Fasting serum TG only;
- Explain importance of continued adherence to a stable, heart-healthy diet and limited alcohol intake;
- Initiate wash-out; and
- Assess adverse events (AEs that occur prior to the first dose of study drug [Study Day 1] should be reported as an update to medical history as well as be reported on the appropriate adverse event eCRF) and concomitant medications.

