### 9.3.2 Analysis of Safety

Safety will be assessed using the SAS. The assessment of safety will include adverse events, clinical laboratory assessments, ECGs, physical examinations, and vital signs. In addition, the safety assessment will be based primarily on the frequency of new or worsening adverse events, laboratory abnormalities, and serious adverse events (SAEs). Other safety data will be summarized as appropriate.

AEs will be coded using the most recent version of the Medical Dictionary for Regulatory Activities (MedDRA). The summarization of AEs will include only treatment-emergent AEs (TEAEs), defined as AEs that begin or worsen after randomization and ingestion of the first dose of study drug. TEAEs and SAEs will be summarized by system organ class (SOC), severity, and relationship to study drug for each treatment group. Deaths, withdrawal from study treatment due to AEs, and withdrawal from the study due to AEs will each be summarized by treatment group.

Safety laboratory data will be summarized by treatment group at baseline, and at each post-baseline time point, if applicable, and change from baseline to End of Treatment (Week 12) or the ET Visit, if applicable. Baseline for safety laboratory data will be defined as the last pre-dose value (pre-dose Study Day 1/Visit T1 or prior). Frequency counts of new or worsening abnormalities will also be provided.

Vital signs data (value and change from baseline, where appropriate) will be summarized by treatment group at baseline and at each post-baseline time point. Baseline for vital signs data will be defined as the last pre-dose value (pre-dose Study Day 1/Visit T1 or prior). Abnormalities in ECGs and in PEs will be summarized.

All safety data will be listed.

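### The SAP counts a treatment-emergent event by start date alone and lets pre-dose SAEs into the by-arm SAE tables; neither departure from the protocol is declared

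*SAP*

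**What the plan says.** **Protocol 9.3.2 (same text in the synopsis).** The safety assessment rests mainly on the frequency of new or worsening AEs, laboratory abnormalities and SAEs. On scope it says "The summarization of AEs will include only treatment-emergent AEs (TEAEs"), and these are "defined as AEs that begin or worsen after randomization and ingestion of the first dose of study drug". The next sentence reads "TEAEs and SAEs will be summarized by system organ class (SOC), severity, and relationship to study drug for each treatment group".

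**SAP 12.1.** The rule for a treatment-emergent AE (TEAE) is: "A TEAE is defined as an AE with start date on or after the first dose date and less than 30 days" (counted from the final dose). There is no worsening limb. The overview table and the "summaries of serious adverse events (SAEs) and AEs resulting in death (both of which will include all AEs") are exempt from the TEAE restriction. The tables are by treatment group. The overview is to be given separately for the double-blind and follow-up periods. Anything that is not a TEAE is flagged as such in the AE listing.

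**What reaches the AE form before dosing.** Protocol 6.2 and 6.3.1 say that AEs before the first dose "should be reported as an update to medical history as well as be reported on the appropriate adverse event eCRF". Protocol 6.3.2, 6.3.3, 8.1 and Appendix A footnote v give the same instruction for SAEs only. Protocol 8.1 adds that a pre-existing condition that changes in severity, frequency or seriousness after the first dose is to be reported as an AE. It does not say whether the start date is the original onset or the date of worsening.

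**SAP 4.3.** Five changes from the protocol are listed. None concerns the TEAE definition or the scope of the SAE tables.

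**The concern.** The two rules move counts in opposite directions. The start-date rule can leave out a worsening on drug, which the protocol names as part of its main safety measure. Such an event would be missing from every TEAE table, including those for related events, maximum severity and treatment discontinuation. The all-AE rule can put into an arm's SAE count an event that happened before the subject had taken any study drug.

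The arms are small and SAEs were rare in earlier studies, so one misplaced subject is visible in the table. Because the SAP does not declare either change, a reader of the results would assume that the protocol's definition was used.

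**Working it through.** The documents give no figure to reproduce. The check compares the rules on the cases that can arise, then puts a scale on one event.

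**Step 1: worsening.** Four ways of recording an event that predates dosing and worsens on treatment:

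- A. The condition is in medical history and the site opens an AE dated at the worsening. It is a TEAE under the protocol and under the SAP.
- B. The condition is in medical history and the site opens an AE dated at the original onset. It is a TEAE under the protocol but not under the SAP.
- C. The event is already on the AE form before dosing and the record is updated in place. It is a TEAE under the protocol but not under the SAP.
- D. The event is already on the AE form and the worsening is entered as a new, later-dated record. It is a TEAE under both.

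The rules differ in B and C. The documents do not say which practice sites follow. How often C can occur also depends on the unresolved conflict over pre-dose entries: under Protocol 6.2 and 6.3.1 it can involve any AE, under the other sections only SAEs.

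**Step 2: pre-dose SAEs.** The Safety Analysis Set (SAP 8.3) contains randomized subjects with at least one dose. An SAE in wash-out or screening, in a subject who is later dosed and does not worsen, is not a TEAE under either document. Under SAP 12.1 it still enters the SAE table by system organ class and preferred term, in the arm later assigned. In the overview it has no defined place, because that table is split only into double-blind and follow-up periods.

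**Step 3: scale.**

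- Arm size is 30 (SAP 9.1). One subject with a pre-dose SAE adds 1/30 = 3.3 percentage points to that arm; two add 2/30 = 6.7.
- Protocol 1.4 gives the background: "Ten subjects (1%) reported a treatment-emergent serious adverse event (SAE) across all previous studies", out of 895 exposed. That is 10/895 = 1.1%.
- If that frequency carried over, the expected number per arm is 30 × 10/895 = 0.34, and the chance of at least one is 1 − (1 − 10/895)^30 = 29%. A single pre-dose SAE could then be an arm's whole SAE count.
- Time before dosing runs at most from Day -84 to Day -1 (SAP Table 1), or 84/7 = 12 weeks, for the longest wash-out. Subjects without wash-out have 14 to 28 days (Protocol 3.1).

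The 1.1% is an on-treatment frequency pooled over earlier studies. It shows how few SAEs to expect, not how often a pre-dose SAE occurs in someone who is still randomized. The documents give no figure for that.

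**The case against.** **Worsening is handled at data capture.** Protocol 8.1 already requires a worsened condition to be reported as an AE, and most of the protocol sends only pre-dose SAEs to the AE form. On that reading the one-record problem shrinks to pre-dose SAEs that worsen, and the all-AE rule already counts those in the SAE tables. A reader might infer that the SAP drops all worsening events; the documents do not support that. What stands is narrower: with no rule on the start date, the SAP's result depends on site practice.

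**The protocol may allow all SAEs.** It names SAEs beside TEAEs in the sentence on summaries. That leaves some ambiguity. But the sentence before it restricts AE summaries to TEAEs, and nothing there extends the tables to time before dosing.

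**The all-AE rule keeps late SAEs.** This is correct and matters for the remedy. Protocol 8.3 expects reports of related SAEs arising after the 30-day follow-up. Ending the SAE tables at the Follow-up Visit would lose them.

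**Bias and attribution.** A reader might infer that the rule biases the comparison of arms or attributes pre-dose events to drug. It does not bias: pre-dose events are independent of the arm later assigned, so any imbalance is chance. Related SAEs are tabulated separately, and the causality guidance in Protocol 8.1.3 expects the event to follow dosing. Many subjects with a pre-dose SAE may also fail screening.

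**Deaths and the 30-day cut.** A reader might extend the point to deaths, but no one in the Safety Analysis Set can have died before dosing. A reader might also object that the cut (last included day 29) ends before the latest follow-up call (28 + 3 = day 31). SAEs and deaths are exempt from the cut, so only non-serious events starting on days 30 to 31 are affected. That is trivial.

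**Conclusion.** The point holds as two undeclared departures in counting rules. The SAP's TEAE definition omits the worsening limb, and its by-arm SAE tables admit events from before first dose.

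The first can lose events only if the original start date is kept or a pre-dose record is updated in place; its size is unknown. The second is worth 3.3 percentage points per affected subject, assuming 30 dosed subjects per arm. Its frequency is also unknown, and its effect is noise rather than systematic bias. The reading of the protocol rests on giving weight to its restriction of summaries to TEAEs over the less clear sentence that follows.

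Neither departure touches the efficacy analysis. Both rules can misclassify events in safety tables with very small counts, and both are cheap to correct.

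**What to change.** 1. In SAP 12.1, define a TEAE as an AE that starts, or worsens in severity or seriousness, on or after first dose. For a worsened event, use the date of worsening as the start date.
2. Build the by-arm SAE tables on SAEs that start or worsen on or after first dose, with no upper time limit, so that late SAEs stay in. Keep all deaths reported. Show pre-dose SAEs in the flagged listing that is already planned, or in a separate pre-treatment row. Changes 1 and 2 belong together: without the worsening limb, change 2 would remove a pre-dose SAE that worsens on treatment.
3. Declare both in SAP 4.3. Reconcile Protocol 6.2 and 6.3.1 (all AEs) with 6.3.2, 6.3.3, 8.1 and Appendix A footnote v (SAEs only) on which pre-dose events go on the AE form.

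The cost is SAP wording and a small derivation change. The date of worsening must be identifiable in the data; the documents do not show whether the form captures it when a record is updated in place. The downside is that pre-dose SAEs leave the arm totals, though they stay visible in the listing or the separate row.
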